#### ***3.1.5.2 CHOP-INTEND Total Score***

The CHOP-INTEND assessment contains 16 items, 13 of them are tested on both right side and left side. The item score will be equal to the maximum score of both sides for those 13 items. If the score for one side is missing the item score will be equal to the score of the non-missing side.

If not all tests were performed at a visit, the approach described below will be used for the handling of missing data. Missing data will be imputed on an individual item level. If a test is missing at screening, then the missing test will be imputed as the median of the non-missing values of the group to which the subject belongs: age at symptom onset ( $\leq 2$  weeks,  $>12$  weeks) by disease duration ( $\leq 2$  weeks,  $>12$  weeks). If for the subject with the missing test, the corresponding visit is flanked by visits with non-missing tests, the missing test will be imputed using linear interpolation with the result rounded to the nearest integer score. Otherwise, the missing test will be imputed as the lowest score of the visit in the group (age at symptom onset by disease duration) to which the subject belongs. If the group is empty, the missing test will be imputed as the lowest score of all available subjects of the visit.

### 3.1.5.3 Ventilator Use

If data indicates a patient requires BiPAP or CPAP daily, but the number of hours ventilator use is missing then the missing value will be imputed using the greater requirement of the visits that flank the missing visit(s).

## 3.2 Primary Efficacy Analysis

Motor milestones will be assessed using Section 2 of the Hammersmith Infant Neurological Exam (HINE) which is comprised of eight independent milestone categories: voluntary grasp, ability to kick in supine position, head control, rolling, sitting, crawling, standing, and walking. Within each of these categories, subjects can progress from complete inability to perform a motor task, for example no grasp, no kicking, unable to maintain head upright, all the way to complete mastery of each category, for example achievement of pincer grasp, touching toes while supine, maintaining their head upright for a maximum of 26 motor milestones (see Table 2 below).

Table 2. Motor Milestone Achievement (Module 2, HINE)

Motor milestone	Milestone progression				
	No grasp	Uses whole hand	Finger and thumb; immature grasp	Pincer grasp	→
Voluntary grasp					
Ability to kick (in supine)	No kicking	Kicks horizontal; legs do not lift	Upward (vertically)	Touches leg	Touches toes
Head control	Unable to maintain upright	Wobbles	All the time upright		
Rolling	No rolling	Rolling to side	Prone to supine	Supine to prone	
Sitting	Cannot sit	Sit with support at hips	Props	Stable sit	Pivots (rotates)
Crawling	Does not lift head	On elbow	On outstretched hand	Crawling flat on abdomen	On hands and knees
Standing	Does not support weight	Supports weight	Stands support	with	Stands unaided
Walking	No walking	Bouncing	Cruising (holding on)	Walking independently	

For each dosing visit, in addition to the scheduled pre-dose assessment, the HINE including motor milestones are also assessed at 3, 6 hours and 1 day after dosing to monitor patient safety. Since the patient's motor function could be temporarily impacted by the lumbar puncture procedure, only the motor milestone results from the pre-dose assessment will be

used for the efficacy analysis and the results at 3, 6 hours and 1 day after dosing will be excluded.

The improvement in motor milestones is defined as achievement of any of the following :

- (i) at least a 2-point increase from baseline or achievement of pincer grasp in the category of voluntary grasp, or
- (ii) at least a 2-point increase in the ability to kick or achievement of touching toes, or
- (iii) a 1-point increase in any of the remaining 6 categories: head control, rolling, sitting, crawling, standing, or walking.

Subjects who die or withdraw from the study will be counted as non-responders and will be included in the denominator for the calculation of the proportion. As a result, mortality will be accounted for in the motor milestone analysis. For subjects on permanent ventilation, because motor milestone assessment continues, functional scores after permanent ventilation will be used to assess improvement in motor milestones.

The primary analysis will be the proportion of subjects who achieve improvement in motor milestones at their last available visit. It will be tabulated by cohort and overall. The primary analysis will be conducted using the Evaluable Population.

As the sensitivity analyses, the proportion of subjects who achieve improvement in motor milestones at their last available visit will be tabulated

- 1). by cohort and overall using the 2 SMN2 Copy Set
- 2). by cohort and overall using the Safety Population
- 3). by SMA subtype using the Safety Population

In addition, the following analyses will also be conducted to assess effects of treatment with ISIS 396443 on the motor milestone improvement over time:

- The proportion of subjects who achieve improvement in motor milestones will be tabulated by visit.

Subjects who die or withdraw from the study prior to a visit will be counted as non-responders for the visit and all subsequent visits and will be included in the denominator for the calculation of the proportion. As a result, mortality will be accounted for in the motor milestone analysis. For subjects on permanent ventilation, because motor milestone assessment continues, functional scores after permanent ventilation will be used to assess improvement in motor milestones.

If a subject misses a visit and has visit(s) beyond the visit, then the subject will be counted as a non-responder and included in the denominator for the calculation of the proportion for the visit.

Subjects who are ongoing in the study and haven't reached a visit will not be included in the denominator for the calculation of the proportion for the visit and all subsequent visits.

- The proportion of subjects who achieve full head control (defined as All the Time Upright), independent sitting (defined as either Prop, Stable Sit or Pivot), rolling (Prone to Supine or Supine to Prone), crawling (defined as crawling On outstretched hand, flat on abdomen, or On hands and knees), standing (defined as Stands with support or Stands unaided), or walking (Cruising (holding on) or Walking independently) at their last available visit. Subjects who die or withdraw from the study will be counted as non-responders and will be included in the denominator for the calculation of the proportion. For subjects on permanent ventilation, because motor milestone assessment continues, functional scores after permanent ventilation will be used to assess improvement in motor milestones.
- The proportion of subjects who achieve full head control (defined as All the Time Upright), independent sitting (defined as either Prop, Stable Sit or Pivot), rolling (Prone to Supine or Supine to Prone), crawling (defined as crawling On outstretched hand, flat on abdomen, or On hands and knees), standing (defined as Stands with support or Stands unaided), or walking (Cruising (holding on) or Walking independently) will be tabulated by visit. Subjects who die or withdraw from the study prior to a visit will be counted as non-responders for the visit and all subsequent visits and will be included in the denominator for the calculation of the proportion. For subjects on permanent ventilation, because motor milestone assessment continues, functional scores after permanent ventilation will be used to assess improvement in motor milestones.

If a subject misses a visit and has visit(s) beyond the visit, then the subject will be counted as a non-responder and included in the denominator for the calculation of the proportion for the visit. Subjects who are ongoing in the study and haven't reached a visit will not be included in the denominator for the calculation of the proportion for the visit and all subsequent visits.

- Summary of change from baseline in the motor milestone total score at their last available visit. The total motor milestone score equals to the sum of individual scores. For example, if the subject cannot maintain head control this is scored as 0, head wobbles as 1, and all the time upright as 2. Complete inability to perform any motor task will therefore be as zero. The ability to master all motor milestones will be scored as 26.
- Summary of change from baseline in the motor milestone total score by visit.

The above analyses will be tabulated

- 1). by cohort and overall using the Evaluable Population
- 2). by cohort and overall using the 2 SMN2 Copy Set

- 3). by cohort and overall using the Safety Population
- 4). by SMA subtype using the Safety Population

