#### ***10.5.3 Safety and Pharmacokinetic Analysis***

All subjects exposed to ISIS 396443 will be included in the safety analyses.

Treatment duration and amount of Study Drug received will be summarized by dose cohort. Subject incidence rates of all adverse events will be tabulated by Medical Dictionary for Regulatory Activities (MedDRA™) system organ class, and by MedDRA™ term. Tables and/or narratives of “on-study” deaths, serious and significant adverse events, including early withdrawals due to adverse events, will also be provided.

All treatment emergent AEs, all treatment emergent AEs potentially related to Study Drug, all treatment emergent serious AEs, and all treatment emergent serious AEs potentially related to Study Drug will be summarized.

Laboratory tests including chemistry panel, complete blood count with differential, urinalysis, and CSF components will be summarized by study visit for each dose cohort. These safety variables will also be presented over time after Study Drug administration, as appropriate, using results prior to Day 1 dosing as Baseline. Vital sign results will be presented similarly.

Physical and neurological examination findings and results from ECG will be listed for review. As appropriate, results will also be summarized descriptively for each dose cohort. Concomitant medication usage for each subject will be listed for review. Plasma pharmacokinetic parameters and ISIS 396443 concentrations in plasma and CSF for the Pharmacokinetic population will be summarized by dose cohort using descriptive statistics and, where warranted, presented graphically.

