## Appendix A – Schedule of Procedures for ‘Maintenance’ Dosing Period, Visits Only\*

\* Note that monitoring telephone calls will also occur on Study Days 274 ( $\pm 3$ ), 295 ( $\pm 3$ ), 316 ( $\pm 3$ ), 358 ( $\pm 3$ ), 400 ( $\pm 3$ ), 421 ( $\pm 3$ ), 463 ( $\pm 3$ ), 484 ( $\pm 3$ ), 526 ( $\pm 3$ ), 547 ( $\pm 3$ ), 589 ( $\pm 3$ ), 610 ( $\pm 3$ ), 652 ( $\pm 3$ ), 673 ( $\pm 3$ ), 715 ( $\pm 3$ ), 736 ( $\pm 3$ ), 778 ( $\pm 3$ ), 799 ( $\pm 3$ ), 841 ( $\pm 3$ ), 862 ( $\pm 3$ ), 904 ( $\pm 3$ ), 925 ( $\pm 3$ ), 967 ( $\pm 3$ ), 988 ( $\pm 3$ ), 1030 ( $\pm 3$ ), 1051 ( $\pm 3$ ), 1093 ( $\pm 3$ ), 1114 ( $\pm 3$ ), 1156 ( $\pm 3$ ), 1177 ( $\pm 3$ ), 1219 ( $\pm 3$ ), 1240 ( $\pm 3$ ), 1282 ( $\pm 3$ ), 1303 ( $\pm 3$ ), and 1324 ( $\pm 3$ ) (i.e., approximately every 3 weeks)

Study Period	Dosing/Followup									
	D253 Injection ( $\pm 7$ D)			D254	D337 ( $\pm 7$ D)	D379, 505, 631, 757, 883, 1009, 1135, and 1261 Injection ( $\pm 7$ D)			D380, 506, 632, 758, 884, 1010, 1136, 1262	D442, 568, 694, 820, 946, 1072, 1198 ( $\pm 7$ D)
Study Day	Pre-dose	LP	Post-dose			Pre-dose	LP	Post-dose		
Study Drug: LP Injection 		X 					X 			
Vital Signs 	X		4X 	X	X	X		4X 		X
Weight	X				X	X				X
Growth Parameters 	X 				X	X 				X
Physical Examination	X				X	X				X
Ventilator Use	X				X	X				X
Neurological Examination	X		2X 	X	X	X		2X 		X
ECG					X					X 
Safety Labs 	X 				X					X
Immunogenicity 	X 				X					X
CSF Safety 	X					X				
CSF PK 	X					X				
Plasma PK 	X 					X 				X
CHOP INTEND	X 				X	X 				X
HFMSE 						X 				X
CMAP	X 				X					X
Phone Contact									X	
Con Med Recording	X	X	X	X	X	X	X	X	X	X
Adverse Event Collection	X	X	X	X	X	X	X	X	X	X

- 1 Resting blood pressure, pulse, respiratory rate, temperature, and pulse oximetry awake
- 2 Vital signs performed 1, 2, 4, 6 hours after dosing
- 3 Length, weight for age/length, head circumference, chest circumference, head to chest circumference ratio, arm circumference
- 4 Neurological exams at 3 and 6 hours after dosing
- 5 Serum chemistry, hematology, urinalysis panels (see Appendix B for analytes)

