### **3.6.7 Hammersmith Infant Neurological Examinations – Sections 1 and 3**

Adverse changes in neurological examinations that are deemed clinically significant by the investigator will be classified as adverse events. Data collected for HINE sections 1 and 3 will be provided in a data listing.

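### Post-dose motor milestone scores, collected for safety, have no listing or summary in the SAP, so a transient motor loss after an injection is reported only if an investigator records it as an adverse event

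*SAP*

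**What the plan says.** SAP 3.2 says that at each dosing visit, besides the pre-dose assessment, "the HINE including motor milestones are also assessed at 3, 6 hours and 1 day after dosing to monitor patient safety". The reason for setting these results aside begins "Since the patient's motor function could be temporarily impacted by the lumbar puncture procedure", and the section concludes that only pre-dose results will be "used for the efficacy analysis and the results at 3, 6 hours and 1 day after dosing will be excluded".

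The SAP's safety section on this examination is 3.6.7. Its title and its listing are confined to two of the three HINE sections: "Data collected for HINE sections 1 and 3 will be provided in a data listing". The same section gives a second route: "Adverse changes in neurological examinations that are deemed clinically significant by the investigator will be classified as adverse events". That sentence is not limited to particular HINE sections.

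The protocol is broader. Section 6.2.3 defines the neurological examination as the HINE and places the motor milestones in its Section 2. Section 6.2.11 names the HINE as a safety evaluation. Section 10.5.3 says "Physical and neurological examination findings and results from ECG will be listed for review" and adds a descriptive summary by dose cohort as appropriate. None of these excludes Section 2.

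**The concern.** The post-dose scores are removed from efficacy on the ground that they serve safety, but the safety part of the SAP does not pick them up. A programmer working from the SAP would produce a listing of Sections 1 and 3 and stop there.

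What is lost is a small or short-lived fall in motor function after an injection that the investigator does not consider clinically significant. The study report could not say how often scores fell from the same-day pre-dose value, or whether they came back. For the other safety evaluations in protocol 6.2.11 the SAP does not rest on investigator judgement alone: laboratory values get shift tables, QTcF gets threshold counts, vital signs and physical examinations are listed, and concomitant medications are summarised.

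**Working it through.** The plan states no figure on this point, so there is none to reproduce. The check is a cross-reading followed by a count.

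**1. Where a post-dose Section 2 score could appear**

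| Place | Covers post-dose Section 2 scores? |
|---|---|
| SAP 3.2, efficacy | No, excluded by rule |
| SAP 3.6.7, HINE listing | No, Sections 1 and 3 only |
| SAP 3.6.7, adverse changes | Only as an adverse event, if judged clinically significant |
| SAP 3.6.1 | As an adverse event only, including a lumbar-puncture-related summary |
| SAP 3.6.1.2 | As an adverse event only, including the first 24 h and 72 h after dosing |
| Protocol 10.5.3 with 6.2.3 | Yes, listed, and summarised as appropriate |

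No SAP section gives an output based on the scores. CHOP INTEND cannot stand in, because Appendix A schedules none after an injection.

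**2. Number of examinations concerned (Appendix A)**

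- Injections: 3 loading + 9 maintenance = 12.
- Same-day post-dose examinations: the schedule's footnote is "Neurological exams at 3 and 6 hours after dosing", so 2 × 12 = 24.
- Next-day examinations: Days 2, 16, 86 and 254 = 4.
- Post-dose total per completer: 24 + 4 = 28.
- Examinations kept for efficacy: 12 pre-dose + 12 others (screening, Days 29, 92, 169 and 337, and seven visits from Day 442 to Day 1198) = 24. Day 1352 would make 25; its column is not visible in the text available.
- Share without a score-based output: 28 / (28 + 24) = 54%.
- Ceiling across the study: 28 × 8 = 224; 28 × 20 = 560.

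**3. Wording on the next-day examination**

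Read literally, SAP 3.2 implies 3 × 12 = 36 post-dose examinations per completer. Appendix A gives 28. The difference of 8 is the day after each of the last eight doses (Days 380, 506, 632, 758, 884, 1010, 1136 and 1262), for which Appendix A shows telephone contact and no neurological examination.

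**4. Is there a comparator?**

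Yes. Every injection has a pre-dose neurological examination. In the maintenance schedule that row does not carry the footnote allowing some assessments up to 7 days before dosing, so the comparison is with the same day.

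**5. When would the efficacy tables next see the infant?**

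Days from each injection to the next examination kept for efficacy: Day 1 to 15 = 14; 15 to 29 = 14; 85 to 92 = 7; 253 to 337 = 84; 379 to 442 = 63, and likewise 63 after each injection up to Day 1135 (1198 − 1135 = 63); 1261 to 1352 = 91, if Day 1352 includes the examination. A loss that resolves within 7 to 91 days leaves no trace in the by-visit milestone tables.

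**The case against.** The strongest case is that the gap is narrow and the protocol already covers it.

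- **Adverse events.** A reader might infer that acute motor loss is analysed nowhere. The documents do not support that. Clinically significant change becomes an adverse event, and SAP 3.6.1 and 3.6.1.2 plan summaries aimed at lumbar-puncture-related and early post-dose events. This stands, but every one of those outputs depends on the investigator's initial judgement.
- **Lasting loss.** Milestone response and total score are tabulated by visit, including in the Safety Population, so a loss still present at the next scheduled examination would enter those group summaries. This stands; what remains is transient loss.
- **Protocol listing.** Protocol 10.5.3 promises a listing and the SAP does not withdraw it. The SAP also names no listing for pre-dose Section 2, CHOP INTEND or CMAP, so silence proves little. This stands in part. Those measures have planned summaries, while post-dose Section 2 has neither, and 3.6.7 is an express restriction rather than silence. Summary under 10.5.3 is only as appropriate, so lacking a table is no breach.
- **A named risk.** A reader might take SAP 3.2 to identify acute motor deterioration from the drug as a known risk. It does not. It says the procedure may affect function for a time, as a reason why the scores are hard to interpret.
- **Value of a table.** Sedation is permitted, infants are encouraged to lie flat for an hour after dosing, and there is no control arm, so a 1-point fall may be noise. A comparison of 6 mg with 12 mg would say almost nothing: 4 infants × 3 doses = 12 occasions at 6 mg, against at most 16 × 12 + 4 × 9 = 228 at 12 mg, with dose level confounded with dose number. This stands. It argues for a descriptive table with footnotes and no dose comparison; it does not argue against reporting the scores.

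**Conclusion.** The point holds in a limited form. Post-dose Section 2 scores have no listing or summary in the SAP, and SAP 3.6.7 is narrower than protocol 10.5.3 read with 6.2.3. A transient motor loss after an injection is therefore visible only through an investigator-reported adverse event. Excluding the scores from efficacy is reasonable and should stay.

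The size is 28 scheduled examinations per infant completing all 12 injections. The totals of 224 and 560 are ceilings: they assume that 8 or 20 infants complete every injection and that each scheduled post-dose neurological examination includes Section 2, as SAP 3.2 says. They count examinations without a planned output and do not measure harm.

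Neither the primary endpoint nor any efficacy result is affected. The next-day mismatch between SAP 3.2 and Appendix A is a matter of wording and changes no result, because next-day scores are excluded wherever they exist. The point is still worth correcting, since following 3.6.7 as written leaves part of a safety assessment made at every injection unreported.

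**What to change.** 1. Extend SAP 3.6.7, title and text, to HINE Section 2, and list all post-dose Section 2 results in the Safety Population.
2. Add one descriptive table, by cohort and overall, of change in the Section 2 total from the same-day pre-dose score at 3 h, at 6 h, and on the next day where scheduled. Include the number of infants losing at least 1 point in any category, and whether the loss had recovered by the next scheduled visit.
3. Make no inferential comparison of 6 mg with 12 mg. Footnote sedation, procedure effects and test noise.
4. Reconcile the statement in SAP 3.2 that a 1-day examination follows each dosing visit with Appendix A, which shows a next-day neurological examination only on Days 2, 16, 86 and 254.

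The cost is SAP wording, one listing and one table from data already collected. The downside is that some of the falls shown will be noise or procedure effect, which the footnotes should make clear.

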## **8.8 Discontinuation of Study Treatment**

A subject must permanently discontinue study treatment for any of the following:

- The subject withdraws consent
- The subject experiences an adverse event that necessitates permanent discontinuation of study treatment
- The subject experiences a DLT as defined in Section 3.7

The reason for discontinuation of study treatment must be recorded in the Case Report Form (CRF) and source documentation.

Subjects that discontinue treatment will enter the post-treatment follow-up period unless consent is withdrawn (see Appendix A).

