### **10.3 Populations**

Safety Population: All subjects who are registered and receive at least one dose of Study Drug.

Pharmacokinetic Population: All subjects who are registered and for which there is at least one evaluable post-dose pharmacokinetic sample.

Efficacy Population: all subjects who are registered, receive all scheduled loading doses of Study Drug (i.e., Days 1, 15 and 85), and complete the Day 92 visit.

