#### 3.1.2 *Subject Population Analyzed*

Safety Population will include all subjects who are registered and receive at least one dose of study drug.

Pharmacokinetic (PK) Population will include all subjects who are registered and for which there is at least one evaluable post-dose pharmacokinetic sample. The Efficacy Evaluable (Evaluable) Population will include all subjects who are registered, receive all scheduled

loading doses of study drug (i.e., Days 1, 15 and 85), and complete visits through at least Day 92. Two SMN2 Copy Set will include subset of Evaluable Population who have 2 copies of the *SMN2* gene. Safety analyses will be conducted on the Safety Population, PK analyses will be conducted in PK Population, efficacy and biomarker analyses will be conducted on the Evaluable Population and 2 SMN2 Copy Set. In addition to the Safety Population, PK Population and Evaluable Population, it is recognized that some data displays will be provided for “All Screened”, “All Enrolled”, and “Screening Failures” subjects but no data analysis will be executed in these populations.

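### The primary responder proportion excludes infants who die or withdraw before completing loading and Day 92, so the SAP's statement that mortality is accounted for is untrue for them

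*SAP*

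**What the plan says.** SAP 3.2 scores an infant who dies or withdraws as a non-responder and keeps that infant in the denominator. It then draws an unqualified conclusion: "As a result, mortality will be accounted for in the motor milestone analysis". The analysis set follows shortly after: "The primary analysis will be conducted using the Evaluable Population".

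SAP 3.1.2 defines that set as registered infants who receive all scheduled "loading doses of study drug (i.e., Days 1, 15 and 85), and complete visits through at least Day 92". Protocol 10.3 has essentially the same restriction for its Efficacy Population: infants must "receive all scheduled loading doses of Study Drug (i.e., Days 1, 15 and 85), and complete the Day 92 visit". The 2 SMN2 Copy Set is a subset of the Evaluable Population and inherits the condition. The Safety Population needs only registration and one dose.

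SAP 3.1.2 assigns populations to analyses as follows: "efficacy and biomarker analyses will be conducted on the Evaluable Population and 2 SMN2 Copy Set". It does not mention the Safety Population for efficacy. SAP 3.2 nevertheless lists the same responder proportion "by cohort and overall using the Safety Population" among its sensitivity analyses. The supporting milestone analyses and the secondary efficacy analyses are also tabulated in that population.

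**The concern.** Membership of the primary set depends on something that happens after treatment starts, namely surviving and staying in the study for about three months. The non-responder rule can act only on infants who have already qualified. An earlier death or withdrawal cannot lower the primary proportion, although the SAP tells the reader that it does.

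This matters more here than in many trials. Protocol 2.1 describes a disease in which affected children usually die of respiratory failure by age 2, so early death is a realistic outcome. The study is open-label with no control arm, and SAP 3.1.1 calls the primary analysis non-comparative. The reported proportion is therefore itself the main result, and an overstated proportion has no control arm to be set against.

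**Working it through.** **The plan's own figure.** SAP 3.1.3 gives power for 20 patients with a two-sided exact binomial test, alpha 0.05 and a null rate of 5%. With 0.025 in the upper tail, the smallest rejecting count is 4 of 20: P(X ≥ 4) = 0.0159, whereas P(X ≥ 3) = 0.0755. No lower rejection region exists, because P(X = 0) = 0.95^20 = 0.358. Power at true rates of 20, 25, 30 and 35% is 58.9, 77.5, 89.3 and 95.6%. SAP Table 1 has 58, 77, 89 and 95%, so it is reproduced to within one point. It assumes that all 20 infants are analysed.

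**Who is in the primary denominator.**

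- Death or withdrawal after all loading doses and Day 92: in the set, counted as a non-responder.
- Death or withdrawal before that: not in the set. No text in either document restores the infant.
- Alive and in follow-up, but a loading dose missed: not in the set, whatever the motor status.

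Protocol 8.7 lets the third loading dose be delayed to as late as Day 120, so the qualifying period can run beyond Day 92.

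**Effect on the proportion.** Take 20 treated infants, r responders, and k early deaths or withdrawals, none of them a responder. The all-treated rate is r/20, the evaluable rate is r/(20-k), and their ratio is 20/(20-k). The documents do not give k; the range 0 to 4 is an assumption. At k = 0 the two rates are equal.

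| Responders | All treated | k = 1 | k = 2 | k = 3 | k = 4 |
|---|---|---|---|---|---|
| 6 | 30.0% | 31.6% | 33.3% | 35.3% | 37.5% |
| 10 | 50.0% | 52.6% | 55.6% | 58.8% | 62.5% |
| 13 | 65.0% | 68.4% | 72.2% | 76.5% | 81.3% |

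The primary table is also split by cohort. In Cohort 1 (n = 4), one early loss moves 2 responders from 2/4 = 50.0% to 2/3 = 66.7%.

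**Direction for infants who stop dosing but stay in follow-up.** Protocol 8.8 says: "Subjects that discontinue treatment will enter the post-treatment follow-up period unless consent is withdrawn". Such an infant can still respond. If one of 10 responders among 20 stops during loading, the evaluable rate is 9/19 = 47.4% against 10/20 = 50.0%. The restriction then lowers the rate.

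**Effect on the test against 5%.** For 16, 17, 18, 19 and 20 evaluable infants, P(X ≥ 4) is 0.0070, 0.0088, 0.0109, 0.0132 and 0.0159. P(X ≥ 3) runs from 0.0429 (n = 16) to 0.0755 (n = 20), always above 0.025. The threshold is 4 responders throughout. When the infants lost early are non-responders, the choice of set does not change whether a given count rejects 5%.

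**The case against.** The plan already contains most of the remedy. The same proportion is pre-specified in the Safety Population, by cohort and overall, and there every treated infant who dies or withdraws counts as a failure. SAP 3.3.1 also analyses death or permanent ventilation as a separate endpoint timed from birth, again including the Safety Population. Both documents state the evaluable restriction openly. Within the primary set, the non-responder rule works from qualification to Day 1352, which is most of the follow-up. An evaluable set also answers a legitimate question about infants who completed loading.

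The size is hypothetical as well: k may be 0. Protocol 4.3 allows some early withdrawals to be replaced. If k losses were replaced to reach 20 evaluable infants, the factor would be (20+k)/20, or 1.20 at k = 4, instead of 1.25. Finally, SAP 3.1.2 does not expressly exclude the Safety Population from efficacy analyses, and the later sections name it clearly enough that a programmer would not be misled.

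These points limit the severity: the gap would be visible to anyone who compares the two tables, and the inference against 5% is unaffected. They do not make the mortality sentence true of the primary analysis. They also leave the 2-copy tables without an all-treated counterpart. Replacement changes the factor slightly, but the replaced infant still disappears from the primary proportion.

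**Conclusion.** The concern holds. The SAP's stated rule and its primary analysis set are incompatible for infants who die or withdraw before completing loading and Day 92. For such losses the primary proportion is overstated or unchanged, never understated. With 20 treated infants, no replacement, non-responding early losses and an assumed k of 0 to 4, the factor is 1.00 to 1.25, which is up to 12.5 percentage points at 10 responders. For infants who stop dosing but remain in follow-up, the direction is uncertain. The damage is to the headline estimate and to the accuracy of its description, not to the test. It should be fixed, but because the all-treated analysis is already planned it does not undermine the study.

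**What to change.** - In SAP 3.2, make the Safety Population the primary analysis set, with death or withdrawal at any time after the first dose counted as non-response. Keep the Evaluable Population as a sensitivity analysis. The mortality sentence is then correct for the primary result.
- In SAP 3.1.2, add the Safety Population to the sentence assigning populations to efficacy analyses, and define the 2 SMN2 Copy Set from the Safety Population.
- Align the Efficacy Population in protocol 10.3.
- Report the number of treated infants outside the Evaluable Population, with reasons, beside the primary result.

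The two primary tabulations already exist and change places; the all-treated 2-copy tabulation is new. The rest is wording, although the protocol edit is an amendment, and protocol 12.1 requires the regulatory authority and IRB/REB to be informed of it. The headline rate may be slightly lower, and withdrawals are scored as failures whatever their motor status.

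If the Evaluable Population must stay primary, the minimum is to limit the mortality sentence to losses after qualification, add the Safety Population to SAP 3.1.2, and report the exclusions with reasons. That removes the contradiction but leaves the selection on a post-treatment outcome.
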